# 4 STUDY DESIGN

This is a prospective, multi-center open-label study designed to collect additional data on safety, performance and effectiveness of Phasix™ Mesh for primary ventral or incisional or multiply-recurrent hernia repair. Follow-up visits will be conducted at 1, 3, 6, 12, 18, 24, 30, 36, 42, 48, 54, and 60 months following surgery. See Section 6 for a detailed schedule of study visits and procedures.

# 5 STUDY POPULATION

#### 5.1 Number Of Subjects

This study is projected to enroll up to 120 subjects at approximately 16 US sites.

#### 5.2 Eligibility Criteria – Enrollment Period

#### 5.2.1 Inclusion Criteria

The subject must meet all of the criteria listed below to be enrolled in the study:

- 1. Subject must be 18 years of age or older
- 2. Subject or subject's legally authorized representative must be willing to give written informed consent
- 3. Subject must be diagnosed with primary ventral, incisional hernia or multiplyrecurrent (not to exceed 3 recurrences) ventral or incisional hernia
- 4. Subject must have a hernia greater than  $10 \text{ cm}^2$  and  $\leq 350 \text{ cm}^2$
- 5. Subject must be willing to undergo initial ventral, incisional or multiply-recurrent incisional hernia repair using retro-rectus or onlay placement (using absorbable suture) with or without Component Separation Technique (CST)
- 6. Subject is expected to meet the criteria for a Class I wound as defined by the CDC (Appendix 4)
- 7. Subjects must have 1 or more of the following pre-study conditions:
  - a. Body Mass Index (BMI) between 30-40 kg/m^2, inclusive
  - b. Active smokers (if attempts to quit smoking within two weeks of surgery have failed and the patient is still an active smoker at the time of surgery)
  - c. COPD presence on patient self-report
  - d. Diabetes mellitus
  - e. Immunosuppression
  - f. Coronary Artery Disease
  - g. Chronic corticosteroid use: greater than 6 months systemic use
  - h. Serum albumin less than 3.4 g/dL
  - i. Advanced age: 75 years or older
  - j. Renal insufficiency, defined as serum creatinine concentration  $\geq 2.5 \text{ mg/dL}$

#### 5.2.2 Exclusion Criteria

The subject must be excluded from study enrollment if any of the following criteria are met:

- 1. Subject has had 4 or more previous hernia repairs (of the index hernia)
- 2. The subject has peritonitis
- 3. The subject is on or suspected to be placed on chemotherapy medications during any part of the study
- 4. The subject's Body Mass Index (BMI) is greater than  $40 \text{ kg/m}^2$

- 5. The subject has cirrhosis of the liver and/or ascites
- 6. Subject is American Society of Anesthesiology Class 4 or 5
- 7. Subject is known to be infected with human immunodeficiency virus (HIV)
- 8. Subject has a life expectancy of less than 2 years at the time of enrollment
- 9. Subject has any condition that, in the opinion of the Investigator, would preclude the use of the study device, or preclude the subject from completing the follow-up requirements
- 10. Subject's hernia repair utilizes intra-abdominal mesh placement
- 11. Subject has a surgical wound classified as Class II (Clean-Contaminated), Class III (Contaminated) or Class IV (Dirty-Contaminated) as defined by the CDC (Appendix 4)
- 12. Subject has an active or latent systemic infection
- 13. Subject requires surgical bridge repair as the sole repair
- 14. Subject is pregnant or has plans to become pregnant during the study period or is currently breastfeeding
- 15. Subject has enrolled in another clinical study within the last 30 days
- 16. Subject is part of the site personnel directly involved with this study
- 17. Subject has a known allergy to the test device or component materials (patients with known allergies to tetracycline hydrochloride or kanamycin sulfate should be avoided).

# 5.3 Eligibility Criteria – Extension

5.3.1 Inclusion Criteria

The subject must meet the criteria listed below to be enrolled in the study:

1. Subject or subject's legally authorized representative must be willing to give written informed consent

#### 5.3.2 Exclusion Criteria

The subject must be excluded from study enrollment if any of the following criteria are met:

1. Abdominal surgeries where the index procedure site was cut through

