# 1.2 Rationale

This study is intended to evaluate the use of Phasix™ Mesh for primary ventral, incisional and multiply-recurrent incisional hernia repair amongst subjects at high risk for complications. This protocol version (4.0) is intended to capture longer term data (through 60 months) on all eligible subjects. The protocol's follow up period was not extended due to safety related concerns or trends.

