# 6.1.2 Enrollment

Subjects who sign an informed consent will be considered enrolled in this study. Subjects who provide consent for participation but do not meet all of the study eligibility criteria and do not receive the test device will be considered screen failures.

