# 6.3.3.1 Roll in Visit

The Roll in Visit should be completed in clinic where eligible subjects should be reconsented and confirmed that no abdominal surgeries were performed at the site of the index procedure. Sites with IRB approval of the extension study may complete the Roll in Visit with eligible subjects in combination with the 36 Month Follow Up visit.

6.3.3.2 30 Month Follow Up (910 days  $\pm$  30 days), 42 Month Follow Up (1275  $\pm$  30 days), 54 Month Follow Up (1640 days  $\pm$  30 days)

A telephone contact should be scheduled with the subject and completed by the Investigator. The following information will be collected:

- Symptoms suggestive of hernia recurrence
- Symptoms suggestive of surgical site infections
- Any adverse events relating to the device, procedure, or abdominal space since the last study assessment

If the Investigator determines the responses provided by the subject demands a physical exam be conducted, an office visit will be scheduled. The office visit will be included as part of the 30, 42 or 54 Month Follow Up assessment (not an Unscheduled Visit) and will require all study assessments listed in Section 6.3.3 to be completed.

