#### 6.4 **TABLE OF STUDY EVENTS (cont.)**

Study Procedure	Roll in Visit 	42 Month Visit	48 Month Visit	54 Month Visit	60 Month Visit 	Unschedule d Visit/Early Termination
Visit Window (days)	Re-consent	1275 + 30	1460 + 30	1640 + 30	1825 + 30	
Describe study to subject	X					
Obtain informed consent	X					
Verify eligibility criteria	X					
Collect demographics and medical history						
Conduct physical examination	X		X		X	X
Placement Procedure of Device						
Surgical Pain Scale (VAS)	X		X		X	X
Carolinas Comfort Scale ®	X		X		X	X
SF-12 ®	X		X		X	X
Collect adverse events/ complications	X	X	X	X	X	X
Collect pain medication usage	X		X		X	
Schedule next follow-up visit	X	X	X	X		

 Roll in Visit should be completed in the clinic and may be combined with the 36 Month F/U visit

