# 8 ADVERSE EVENTS

The Investigator is responsible for the detection and documentation of events meeting the criteria and definition of an AE or SAE, as provided in this protocol. All AEs that occur during the study should be treated with established standards of care that will protect the life and health of the study subjects.

AEs will be collected from the time of enrollment (AE onset after signing ICF) through the end of study participation (either study completion or early discontinuation) and will be documented in the medical record or source document and on study eCRFs. All events will be followed to satisfactory resolution or stabilization.

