			
for subgroup analysis by site is defined because the enrollment period had finished.
 
 
The two primary endpoints (hernia recurrence rate and the surgical site infection rate) as well as the rate of reoperations due to index hernia repair are analyzed by disjointed time intervals (Post OP – 1 month/ > 1 month – 3 months/ > 3 months – 6 months/ > 6 months – 12 months/ > 12 months – 18 months/ > 18 months – 24 months/ > 24 months – 30 months/ > 30 months – 36 months) instead of cumulative time intervals post device placement (Until Month 1/ Until Month 3/ Until Month 6/ Until Month 12/ Until Month 18/ Until Month 24/ Until Month 30/ Until Month 36).
 
Some specifications were added.
 

3.0	[name]	21SEP2017	
 
Based on sponsor’s review of TLGs (“dry run”), changes in the SAP 2.0 were requested: 
 
- In the presentation of frequency tables special missing values, as ‘not done’, ‘unknown’, ‘not applicable’, ‘not documented’, should not be merged to the value ‘missing’ but be presented separately.
 
- Some tables should be stratified by gender and visit instead of by visit and gender.
 
- Some listings should be reduced to the “yes”-cases (e.g. SSI=yes).
 
- Some footnotes to tables/listings were added/ modified and variables to listings were added in Appendix A.
 
- Specifications added, typos corrected.
 
- Surgical Procedure time should be calculated in minutes instead of hours.
 
 
 
[name] signs the SAP instead of [name].
 
Criterion (Index hernia repair/ Phasix™ Mesh cut through or a piece of the Phasix™ Mesh removed during a surgery) for exclusion from PP set added.
 
For the hernia recurrence rate, SSI rate and rate of reoperation due to the index hernia repair an overall rate is added to the rates per time interval.
 

4.0	[name]	07AUG2018	
 
New protocol version 4.0 of October 30, 2017: 24 month extension of the study. The changes are effective for sites that approve this protocol change. Sites without an approval proceed according to protocol version 3.0. Visit window for 36 month visits changed
 

Version	Author	Date	Reason for Revision

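### For subjects whose Roll-in visit came after they had completed 36 months, the SAP counts the intervening time as at risk although entry required an uncut index site; late reoperation rates are biased slightly downward, and recurrence rates less so

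*Protocol*

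**What the plan says.** **Entry to the extension.** Protocol 5.3.2 has one exclusion: "Abdominal surgeries where the index procedure site was cut through". Protocol 6.3.3.1 describes the check more broadly: Roll-in is done in clinic, "where eligible subjects should be reconsented and confirmed that no abdominal surgeries were performed at the site of the index procedure".

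**Timing of Roll-in.** Protocol 6.3.3.1 says "Sites with IRB approval of the extension study may complete the Roll in Visit with eligible subjects in combination" with the Month 36 visit, and the note to the second part of the table in Protocol 6.4 says "Roll in Visit should be completed in the clinic and may be combined with the 36 Month F/U visit". Combining is allowed, not required. Where other visits have a day window, that table and the visit list in SAP section 4 give only re-consent for Roll-in. Roll-in does include a physical examination and adverse-event collection.

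**Data capture.** Protocol section 8 collects adverse events until a subject completes or discontinues. The SAP revision history has sites that did not approve version 4.0 continue under version 3.0. Version 4.0 added 24 months to reach 60, so version 3.0 ended at 36.

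**Analysis.** SAP 4.4.1 measures each subject's study duration from Day 0 to one completion, discontinuation or last-visit date. A missed visit followed by a later one does not reduce the interval denominator, and no event is assumed if none is known; SAP section 5 repeats this. SAP 4.4.2 handles reoperation in the same way. The Kaplan-Meier rule has right censoring only. None of these rules mentions Roll-in or the entry condition.

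**The concern.** A subject who finished 36 months and rolled in later contributes the intervening time only because no operation through the index site took place in it. A subject who had such an operation in that time is barred, and follow-up ends at the earlier date. The denominator therefore keeps gap time for those who came through unopened and loses it for those who did not. This is immortal time, and its direction is known: downward.

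Whether the barred subject's operation is recorded at all is unclear. Protocol 6.1.3 collects adverse events for screen failures, but Protocol 6.1.2 uses that term for subjects who "do not meet all of the study eligibility criteria and do not receive the test device will be considered screen failures", and an extension candidate has already received the mesh.

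What is at stake is how the late results are read. Protocol 1.2 says version 4.0 "is intended to capture longer term data (through 60 months) on all eligible subjects", while SAP section 1 says implanted subjects are followed for 60 months. A low reoperation rate just after month 36 could be taken as durability of a resorbable mesh when part of it comes from the entry rule. The rates from month 36 and the 48- and 60-month pain and quality-of-life means also describe only subjects with no reopening before Roll-in, and the SAP does not label them so.

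**Working it through.** The plan states no event rate, hypothesis or sample-size calculation, so it has no figure of its own to reproduce beyond the interval limits. These agree: 1095 + 30 = 1125 and 1275 + 30 = 1305, so the >36-42 month interval is Days 1126-1305.

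**1. Can gaps exist?** Protocol version 4.0 is dated 30 October 2017. The Month 36 window had closed before a site's approval if surgery was at least 1126 days earlier. For approval 0, 90 or 180 days after issue (assumed), that means surgery on or before 30 September 2014, 29 December 2014 or 29 March 2015. The SAP revision entry of 17 December 2015 defines site pooling "because the enrollment period had finished", and SAP 4.2 provides for subjects enrolled before approval of protocol version 2.0, which is dated 3 September 2014. A subject operated on that day reached Day 1125 on 2 October 2017, 28 days before version 4.0. Gaps are plausible; their number cannot be derived.

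**2. Relative size in one interval.** Let q be the true 6-month risk, g the share of the denominator with a gap covering the whole interval, and r the probability that a gap event means the site was cut through before Roll-in. The observed risk in gap subjects is (1 - r)q / (1 - rq), and the pooled rate is (1 - g)q + g(1 - r)q / (1 - rq).

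- r = 1 (every reoperation cuts through the site): gap subjects show 0, and the pooled rate is (1 - g)q. For g = 25%, 50%, 75% it falls by 25%, 50%, 75%.
- r = 0.5, q = 5%: gap subjects show 0.025/0.975 = 2.56%. At g = 50% the pooled rate is 3.78%, a fall of 24%.
- r = 0: no bias.

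A gap covering half the interval roughly halves these falls. The result hardly changes between q = 2% and 10%.

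**3. Absolute size.** All inputs are assumed: 120 subjects, 20% lost by month 36 (96 remain), 20% recurrence risk at 60 months with constant hazard, and reoperation only as immediate repair of a recurrence through the site, with probability p. Monthly hazard = -ln(0.8)/60 = 0.003719; 6-month risk = 2.207%; recurrence-free at month 36 = 87.47%. The fraction eligible for the extension is E = 1 - p(0.1253). The true >36-42 reoperation rate is 0.02207 × p × 0.8747/E; the planned rate is about (1 - share) times that.

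| Case | Gap share, length | p | Eligible | True | Planned | Reoperations missed |
|---|---|---|---|---|---|---|
| a | 10%, 6 mo | 0.5 | 90.0 | 1.03% | 0.93% | 0.09 |
| b | 30%, 6 mo | 0.5 | 90.0 | 1.03% | 0.72% | 0.28 |
| c | 50%, 12 mo | 0.8 | 86.4 | 1.72% | 0.87% | 0.74 |

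Missed reoperations = eligible × share × true rate. In case c about as many are missed again in >42-48. For comparison, one subject is 1/90 = 1.1 points. Recurrence in >36-42 goes from about 2.1% to 1.8% in b and from 2.1% to 1.3% in c.

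**4. Kaplan-Meier for recurrence at 60 months** (true 20%): 1 - exp[-(0.2231 - share × p × gap months × 0.003719)] gives 19.9% (a), 19.7% (b) and 18.6% (c), against a simulated sampling SD of about 4 points.

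**5. What leaving out gap time does.** Simulation with subjects at risk only from Roll-in removes the bias. With q = 5%, g = 50% and gaps uniform over 30-360 days, the ratio of estimated to true reoperation hazard is 0.61 (>36-42) and 0.87 (>42-48) under the plan, and 1.00 in both after correction. The price is precision. With SD = √[rate(1 - rate)/n] and RMSE = √(SD² + bias²), in points for >36-42 reoperation:

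| Case | n, plan | n, gap excluded | SD, plan | SD, gap excluded | RMSE, plan | RMSE, gap excluded |
|---|---|---|---|---|---|---|
| a | 90 | 81 | 1.01 | 1.12 | 1.02 | 1.12 |
| b | 90 | 63 | 0.9 | 1.3 | 0.94 | 1.27 |
| c | 86 | 43 | 1.0 | 2.0 | 1.32 | 1.98 |

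Delayed entry in the Kaplan-Meier behaves alike: mean 20.00% with RMSE 4.04 against 3.93 for the plan in b, and 19.99% with 4.45 against 4.15 in c.

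**The case against.** The strongest case against acting is that the effect is below one subject per interval in a descriptive study, on a secondary endpoint reported without a confidence interval, and that the corrected rate has the larger total error in all three cases. That stands, and it is why the planned rates should remain the main result.

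Several limits also stand. Case c is extreme: with approval at most 180 days after issue and prompt Roll-in, a 12-month gap after Day 1095 needs surgery by about 29 April 2014, and nothing in the documents suggests that half the subjects were that early. Protocol version 4.0 itself plans 60 months for everyone, so the lapse in data collection is an inference about subjects who finished under version 3.0. SAP 4.1 already tabulates subjects per visit and per protocol version, and SAP section 5 discloses the missed-visit rule; neither shows gap lengths or says that entry depended on an unopened site.

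A reader might infer more than the documents support:

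- **That the rate is understated by the full gap share.** This needs every reoperation to cut through the site. SAP 4.4.2 counts all entries on the reoperation page, and under Protocol 5.3.2 an operation that did not cut through the site does not bar entry.
- **That recurrence is affected equally.** An unrepaired recurrence does not bar entry, can be found at the Roll-in examination, and is dated by its adverse-event start. The two biases would be equal only if every gap recurrence were repaired through the site first.
- **That surgical site infection is affected.** Protocol Appendix 3 limits it to 30 days, or one year with an implant, so new infections after month 36 fall outside the classification.
- **That excluding subjects reopened before month 36 is itself a bias.** It defines the cohort; it needs a label, not a correction.

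**Conclusion.** The point holds for subjects whose Roll-in followed 36-month completion, and for no others: a Roll-in combined with Month 36 leaves no gap. For those subjects the SAP treats time that is event-free by selection as ordinary time at risk. Reoperation rates after Day 1125 are biased downward in the intervals that overlap the gap, at most by the gap share. Recurrence rates are biased only through gap recurrences repaired through the site before Roll-in.

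Importance is low. In the illustrative cases the >36-42 month reoperation rate is understated by 0.1 to 0.9 points and the 60-month Kaplan-Meier recurrence estimate by 0.1 to 1.4 points. These sizes rest on assumed risks, losses, gap shares and repair probabilities; only the direction follows from the documents. They do not support a reading that the primary recurrence result is materially wrong, or that a reduced denominator should replace the planned one. They do support disclosing the gaps and showing the corrected rates alongside.

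**What to change.** 1. **Keep** the planned interval rates and Kaplan-Meier analysis as the main analysis.
2. **Add to SAP 4.4.1 and 4.4.2**, only for intervals that start after Day 1125, reoperation and recurrence rates that leave out gap time, with late entrants at risk from Roll-in. Follow-up through 36-month completion is always kept. Add a delayed-entry Kaplan-Meier for recurrence as a sensitivity analysis. State how reoperations recorded at Roll-in but dated in the gap are counted, and likewise recurrences first found there. Leave surgical site infection out of these additions, and count gap events of barred subjects only where they were recorded.
3. **Report** the number barred at Roll-in with reasons, and the number and length of gaps. Label the 36-60 month rates and the pain and quality-of-life means as conditional on no reopening of the index site before Roll-in.
4. **Reconcile** Protocol 5.3.2 with 6.3.3.1, which word the entry condition differently.

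Items 1 to 3 cost some SAP wording, a Roll-in date flag, a supplementary table, one sensitivity run and a disposition row. The downside is noise: the SD of the gap-excluded reoperation rate rises from about 0.9 to 1.3 points at a 30% gap share and from 1.0 to 2.0 at 50%, so these rates are supplementary. If there were no gaps, the disposition row shows it and the added rates equal the planned ones.

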# 6 STUDY PROCEDURES

#### 6.1 Subject Screening and Baseline Evaluation

Subjects with a diagnosis of a primary ventral or incisional hernia or multiply-recurrent hernia requiring surgical repair to close the defect will be screened for potential eligibility against the study protocol inclusion and exclusion criteria, utilizing ordinary standard of care

procedures (e.g. physical examination, blood work, medical evaluation) within 30 days of the date of consent. This may include a full anesthetic work-up customary for hernia repair procedures. Any other standard of care examination or evaluation within 30 days of the date of consent may be considered baseline for study purposes. Prior medical records documenting these tests, examinations and evaluations may be used as the source documents for the baseline visit.

During the screening and recruitment process, the Investigator will be responsible for describing the nature of the clinical study, verifying that the eligibility criteria have been met, and obtaining informed consent. Written informed consent and a Health Insurance Portability and Accountability Act (HIPAA) waiver must be obtained prior to performance of any protocol specific procedures.

The following screening/baseline procedures will be conducted and documented.

#### 6.1.1 Informed Consent

The investigator will explain the study to the subject, answer all of the subject's questions, and obtain written informed consent in a language in which the subject is fluent before the collection of any study data or performance of any study procedures.

The subject (or subject's legally authorized representative) must be willing and able to sign and date the informed consent form (ICF) prior to the collection of study data or performance of any study procedures. The original, signed informed consent will be retained with the subjects' records and a copy provided to the subject.

# 6.1.2 Enrollment

Subjects who sign an informed consent will be considered enrolled in this study. Subjects who provide consent for participation but do not meet all of the study eligibility criteria and do not receive the test device will be considered screen failures.

#### 6.1.3 Eligibility

The subject's eligibility for study enrollment will be reviewed and documented on the appropriate eCRF. At the time of screening, a related progress note must be entered in the source documentation to indicate that all eligibility criteria were reviewed and screening results noted. Final eligibility will be determined intraoperatively.

Subjects who fail to meet eligibility criteria should be considered screen failures and treated according to the Investigator's standard of care. Data are to be collected for screen failure subjects from the time the ICF is signed until the subject is deemed a failure. At a minimum, subject demographics and the reason for failure must be collected; adverse events (AEs) will also be collected and followed through satisfactory resolution or stabilization.

